13.2 When to Report an Event in an Expedited Manner

- Some adverse events require notification **within 24 hours** (refer to Table A) to NCI via the web at <http://ctep.cancer.gov> (email the ADVL1615 COG study assigned Research Coordinator within 24 hours of becoming aware of the event if the CTEP-AERS 24-Hour Notification web-based application is unavailable) and by telephone call to the Study Chair. Once internet connectivity is restored, a 24-hour notification phoned in must be entered electronically into CTEP-AERS by the original submitter at the site.
- When the adverse event requires expedited reporting, submit the report **within 5 or 7 calendar days** of learning of the event (refer to Table A).
- Expedited AE reporting for this study must only use CTEP-AERS (Adverse Event Expedited Reporting System), accessed via the CTEP home page <https://eapps-ctep.nci.nih.gov/ctepaers>.

13.3 Expedited Reporting Methods

13.3.1 CTEP-AERS Reporting

To report adverse events in an expedited fashion use the NCI's Adverse Event Expedited Reporting System (CTEP-AERS) that can be found at <http://ctep.cancer.gov>.

A CTEP-AERS report must be submitted electronically via the CTEP-AERS Web-based application located at <https://eapps-ctep.nci.nih.gov/ctepaers/>. If prompted to enter a sponsor email address, please type in: [contact].

Send supporting documentation by email to the ADVL1615 COG study assigned Research Coordinator. **ALWAYS include the ticket number on all faxed and emailed documents.**

13.4 Definition of Onset and Resolution of Adverse Events

NOTE: These guidelines below are for reporting adverse events on the COG case report forms and do not alter the guidelines for CTEP-AERS reporting.

- 13.4.1 If an adverse event occurs more than once in a course (cycle) of therapy only the most severe grade of the event should be reported.
- 13.4.2 If an adverse event progresses through several grades during one course of therapy, only the most severe grade should be reported.
- 13.4.3 The duration of the AE is defined as the duration of the highest (most severe) grade of the Adverse Effects.
- 13.4.4 The resolution date of the AE is defined as the date at which the AE returns to baseline or less than or equal to Grade 1, whichever level is higher (note that the resolution date may therefore be different from the date at which the grade of the AE decreased from its highest grade). If the AE does not return to baseline the resolution date should be recorded as "ongoing."
- 13.4.5 An adverse event that persists from one course to another should only be reported once unless the grade becomes more severe in a subsequent course. An adverse event which resolves and then recurs during a different course, must be reported each course it recurs.

13.5 Other Recipients of Adverse Event Reports

- 13.5.1 Events that do not meet the criteria for CTEP-AERS reporting ([Section 13.2](#)) should be reported at the end of each cycle using the forms provided in the CRF packet (see [Section 14.1](#)).
- 13.5.2 COG will forward reports and supporting documentation to the Study Chair, to the FDA (when COG holds the IND) and to the pharmaceutical company (for industry sponsored trials).
- 13.5.3 Adverse events determined to be reportable must also be reported according to the

local policy and procedures to the Institutional Review Board responsible for oversight of the patient.

13.6 Reporting Secondary AML/MDS

All cases of acute myeloid leukemia (AML) and myelodysplastic syndrome (MDS) that occur in patients following their chemotherapy for cancer must be reported via CTEP-AERS and included as part of the second malignant neoplasm reporting requirements for this protocol (see data submission packet). Submit the completed CTEP-AERS report within 14 days of an AML/MDS diagnosis occurring after protocol treatment for cancer.

Secondary Malignancy:

A *secondary malignancy* is a cancer caused by treatment for a previous malignancy (e.g., treatment with investigational agent/intervention, radiation or chemotherapy). A secondary malignancy is not considered a metastasis of the initial neoplasm.

CTEP requires all secondary malignancies that occur following treatment with an agent under an NCI IND/IDE be reported via CTEP-AERS. Three options are available to describe the event:

- 1) Leukemia secondary to oncology chemotherapy (e.g., acute myelocytic leukemia [AML])
- 2) Myelodysplastic syndrome (MDS)
- 3) Treatment-related secondary malignancy.

Any malignancy possibly related to cancer treatment (including AML/MDS) should also be reported via the routine reporting mechanisms outlined in each protocol.

Second Malignancy:

A *second malignancy* is one unrelated to the treatment of a prior malignancy (and is **NOT** a metastasis from the initial malignancy). Second malignancies require **ONLY** routine reporting via CDUS unless otherwise specified.

13.7 Reporting Pregnancy, Pregnancy Loss, and Death Neonatal

When submitting CTEP-AERS reports for “Pregnancy”, “Pregnancy loss”, or “Neonatal loss”, the Pregnancy Information Form should be completed and emailed to the ADVL1615 COG study assigned Research Coordinator along with any additional medical information along with any additional medical information. The potential risk of exposure of the fetus to the investigational agent should be documented in the “Description of Event” section of the CTEP-AERS report.

13.7.1 Pregnancy

- Patients who become pregnant on study risk intrauterine exposure of the fetus to agents which may be teratogenic. For this reason, pregnancy occurring on study or within 6 months following the last dose of study therapy should be reported in an expedited manner via CTEP-AERS as “Pregnancy, puerperium and perinatal conditions - Other (Pregnancy) under the Pregnancy, puerperium and perinatal conditions SOC and reported as Grade 3.
- Pregnancy should be followed until the outcome is known. If the baby is born with a birth defect or anomaly, then a second CTEP-AERS report is

required.

13.7.2 Pregnancy Loss (Fetal Death)

- Pregnancy loss is defined in CTCAE version 5.0 as “Death in utero.”
- Any pregnancy loss should be reported expeditiously, as Grade 4 “Pregnancy loss” under the Pregnancy, puerperium and perinatal conditions SOC. Do NOT report a pregnancy loss as a Grade 5 event since CTEP-AERS recognized any Grade 5 event as a patient death.

13.7.3 Death Neonatal

- Neonatal death, defined in CTCAE version 5.0 as “Newborn deaths occurring during the first 28 days after birth” that is felt by the investigator to be at least possibly due to the investigational agent/intervention, should be reported expeditiously.
- A neonatal death should be reported expeditiously as Grade 4 “Death neonatal” under the “general disorders and administration” SOC when the death is the result of a patient pregnancy or pregnancy in partners of men on study.
- Neonatal death should NOT be reported as “Death neonatal” under the General disorders and administration SOC, a Grade 5 event. If reported as such, the CTEP-AERS interprets this as a death of the patient being treated.

Pregnancy should be followed up until the outcome of the pregnancy is known at intervals deemed appropriate by her physicians. The “Pregnancy Information Form” should be used for all necessary follow-ups. This form is available at http://ctep.cancer.gov/protocolDevelopment/electronic_applications/docs/PregnancyReportForm.pdf.

14.0 RECORDS, REPORTING, AND DATA AND SAFETY MONITORING PLAN

14.1 Categories of Research Records

Research records for this study can be divided into three categories:

1. Non-computerized Information: Therapy Delivery Maps, Pathology Reports, Surgical Reports. These forms are uploaded into RAVE.
2. Reference Labs, Biopathology Reviews, and Imaging Center data: These data accompany submissions to these centers, which forward their data electronically to the COG Statistics & Data Center.
3. Computerized Information Electronically Submitted: All other data will be entered in RAVE with the aid of schedules and worksheets (essentially paper copies of the OPEN and RAVE screens) provided in the case report form (CRF) packet.

See separate CRF Packet, which includes submission schedule.

14.2 CDUS

This study will be monitored by the Clinical Data Update System (CDUS) Version 3.0. Cumulative protocol- and patient-specific CDUS data will be submitted electronically to CTEP on a quarterly basis by FTP burst of data. Reports are due January 31, April 30, July 31, and October 31. Instructions for submitting data using the CDUS can be found on the CTEP Web site (<http://ctep.cancer.gov/reporting/cdus.html>).

14.3 Data and Safety Monitoring Plan

Data and safety is ensured by several integrated components including the COG Data and Safety Monitoring Committee.

14.3.1 Data and Safety Monitoring Committee

This study will be monitored in accordance with the Children's Oncology Group policy for data and safety monitoring of Phase 1 and 2 studies. In brief, the role of the COG Data and Safety Monitoring Committee is to protect the interests of patients and the scientific integrity for all Phase 1 and 2 studies. The DSMC consists of a chair; a statistician external to COG; one external member; one consumer representative; the lead statistician of the PEP-CTN scientific committee; and a member from the NCI. The DSMC meets at least every 6 months to review current study results, as well as data available to the DSMC from other related studies. Approximately 6 weeks before each meeting of the Phase 1 and 2 DSMC, study chairs will be responsible for working with the study statistician to prepare study reports for review by the DSMC. The DSMC will provide recommendations to the COG PEP-CTN Chair and the Group Chair for each study reviewed to change the study or to continue the study unchanged. Data and Safety Committee reports for institutional review boards can be prepared using the public data monitoring report as posted on the COG Web site.

APPENDIX I: PERFORMANCE STATUS SCALES/SCORES

Karnofsky		Lansky	
Score	Description	Score	Description
100	Normal, no complaints, no evidence of disease	100	Fully active, normal.
90	Able to carry on normal activity, minor signs or symptoms of disease.	90	Minor restrictions in physically strenuous activity.
80	Normal activity with effort; some signs or symptoms of disease.	80	Active, but tires more quickly
70	Cares for self, unable to carry on normal activity or do active work.	70	Both greater restriction of and less time spent in play activity.
60	Required occasional assistance, but is able to care for most of his/her needs.	60	Up and around, but minimal active play; keeps busy with quieter activities.
50	Requires considerable assistance and frequent medical care.	50	Gets dressed, but lies around much of the day; no active play, able to participate in all quiet play and activities.
40	Disabled, requires special care and assistance.	40	Mostly in bed; participates in quiet activities.
30	Severely disabled, hospitalization indicated. Death not imminent.	30	In bed; needs assistance even for quiet play.
20	Very sick, hospitalization indicated. Death not imminent.	20	Often sleeping; play entirely limited to very passive activities.
10	Moribund, fatal processes progressing rapidly.	10	No play; does not get out of bed.

APPENDIX II: CORRELATIVE STUDIES GUIDE

Correlative Study	Appx.	Sample Volume			Tube Type	
		Volume per sample	Total Volume			
			For subjects ≥ 10 kg	For subjects < 10 kg		
Pharmacokinetics (PK) (required)	X	2 - 3 mL	30 - 45 mL	22 - 33 mL	Vacutainer tubes	
Pharmacodynamics (PD)* (optional)	XI	2 mL	18 mL	18 mL	Yellow-top Citrate vacutainer tubes	
Total Blood Volume			30 - 63 mL	22 - 51 mL		

*Not applicable for patients < 12 months.

APPENDIX III: TOXICITY-SPECIFIC GRADING**Bilirubin**

Grade 1:	> ULN - \leq 1.5 x ULN
Grade 2:	> 1.5 x ULN - 3.0 x ULN
Grade 3:	> 3.0 x ULN -10.0 x ULN
Grade 4:	> 10.0 x ULN

ALT: For the purpose of this study, the ULN for ALT is 45 U/L regardless of baseline.

Grade 1:	> 45 U/L - \leq 135 U/L
Grade 2:	136 U/L - 225 U/L
Grade 3:	226 U/L - 900 U/L
Grade 4:	> 900 U/L

AST: For the purpose of this study, the ULN for AST is 50 U/L regardless of baseline.

Grade 1:	> 50 U/L \leq 150 U/L
Grade 2:	151 U/L -250 U/L
Grade 3:	251 U/L -1000 U/L
Grade 4:	> 1000 U/L

GGT:

Grade 1:	> ULN- 2.5 x ULN
Grade 2:	> 2.5 x ULN - 5.0 x ULN
Grade 3:	> 5.0 x ULN -20.0 x ULN
Grade 4:	> 20.0 x ULN

APPENDIX IV: TEMOZOLOMIDE ORAL CAPSULES DOSING NOMOGRAMSFor the starting dose of 100 mg/m²/dose:

BSA (m ²)	Total pill count	Calculated dose (mg)	Actual dose (mg)
0.2-0.22*	1	20-22	20
0.23-0.27	2	23-27	25
0.28-0.32	3	28-32	30
0.33-0.37	4	33-37	35
0.38-0.42	2	38-42	40
0.43-0.47	4	43-47	45
0.48-0.52	3	48-52	50
0.53-0.57	5	53-57	55
0.58-0.62	3	58-62	60
0.63-0.67	4	63-67	65
0.68-0.72	5	68-72	70
0.73-0.77	6	73-77	75
0.78-0.82	4	78-82	80
0.83-0.87	5	83-87	85
0.88-0.92	6	88-92	90
0.93-0.97	7	93-97	95
0.98-1.02	1	98-102	100
1.03-1.07	2	103-107	105
1.08-1.12	3	108-112	110
1.13-1.17	4	113-117	115
1.18-1.23	2	118-123	120
1.24-1.28	3	124-128	125
1.29-1.33	4	129-133	130
1.34-1.37	5	134-137	135
1.38-1.42	1	138-142	140
1.43-1.47	2	143-147	145
1.48-1.52	3	148-152	150
1.53-1.57	4	153-157	155
1.58-1.62	2	158-162	160
1.63-1.67	3	163-167	165
1.68-1.72	4	168-172	170
1.73-1.77	5	173-177	175
1.78-1.82	1	178-182	180
1.83-1.87	2	183-187	185
1.88-1.92	3	188-192	190
1.93-1.97	4	193-197	195
1.98-3	2	198-300	200

For the reduced dose of 75 mg/m²/dose (75% of starting dose):

BSA (m²)	Total pill count	Calculated dose (mg)	Actual dose (mg)
0.2-0.23	3	15-17.25	15
0.24-0.3	1	18-22.5	20
0.31-0.36	2	23.25-27	25
0.37-0.43	3	27.75-32.25	30
0.44-0.5	4	33-37.5	35
0.51-0.56	2	38.25-42	40
0.57-0.63	3	42.75-47.25	45
0.64-0.7	4	48-52.5	50
0.71-0.76	5	53.25-57	55
0.77-0.83	3	57.75-62.25	60
0.84-0.9	4	63-67.5	65
0.91-0.96	5	68.25-72	70
0.97-1.03	6	72.75-77.25	75
1.04-1.1	4	78-82.5	80
1.11-1.17	5	83.25-87.75	85
1.18-1.23	6	88.5-92.25	90
1.24-1.3	7	93-97.5	95
1.31-1.36	1	98.25-102	100
1.37-1.43	2	102.75-107.25	105
1.44-1.5	3	108-112.5	110
1.51-1.57	4	113.25-117.75	115
1.58-1.64	2	118.5-123	120
1.65-1.7	3	123.75-127.5	125
1.71-1.77	4	128.25-132.75	130
1.78-1.83	5	133.5-137.25	135
1.84-1.9	1	138-142.5	140
1.91-1.97	2	143.25-147.75	145
1.98-3	3	148.5-225	150

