9.4.3 Formulation and Stability

Temozolomide capsules are available in six different strengths (5, 20, 100, 140, 180, 250 mg). The capsules vary in size, color, and imprint according to strength. In the US, capsules are packaged in 5-count and 14-count bottles. In other countries temozolomide may be packaged in 5-count, 14-count or 20-count bottles. Temozolomide capsules are stored at controlled room temperature.

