9.4.4 Guidelines for Administration

See Treatment and Dose Modifications sections of the protocol.

There is a potential for medication errors involving temozolomide capsules resulting in drug overdosages, which may have been caused by dispensing/taking the wrong number of capsules per day and/or product usage exceeding the prescribed dosing schedule.

When dispensing, it is extremely important that prescribing and dispensing include clear instructions on which capsules, and how many of each capsule(s) are to be taken per day. Only dispense what is needed for the course, and clearly indicate how many days of dosing the patient will have and how many days are without temozolomide dosing. When counseling patients, it is important for each patient/parent to understand the number of capsules per day and the number of days that they take temozolomide. It is also important for the patient/parent to understand the number of days that they will be off the medication.

Each strength of temozolomide must be dispensed in a separate vial or in its original container (e.g., bottle or sachet). Based on the dose prescribed, determine the number of each strength of temozolomide capsules needed for the full course as prescribed by the physician. For example, 275 mg/day for 5 days would be dispensed as five 250 mg capsules, five 20 mg capsules, and five 5 mg capsules. Label each container with the appropriate number of capsules to be taken each day. Dispense to the patient/parent, making sure each container lists the strength (mg)

per capsule and that he or she understands to take the appropriate number of capsules of temozolomide from each bottle or vial to equal the total daily dose prescribed by the physician. Institutions that have the capability to dispense temozolomide as daily doses in a blister pack may do so, taking specific precautions to ensure that the appropriate dose is provided and that the patient is educated to understand the daily dosing regimen.

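### Appendix IV, 100 mg/m² temozolomide table: the capsule counts for BSA 0.43-0.47 and 0.48-0.52 m² are transposed (printed 4 and 3, should be 3 and 4)

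*Combined protocol and SAP*

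**What the plan says.** Section 5.1 sets temozolomide at 100 mg/m² per dose, with a maximum of 200 mg, and refers sites to Appendix IV for the capsule nomogram. The Therapy Delivery Maps in Appendix XIII refer to the same place. For each BSA band, Appendix IV gives a total pill count, a calculated dose range and an actual dose in mg.

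In the 100 mg/m² table, the two rows at issue are "0.43-0.47 4 43-47 45" and "0.48-0.52 3 48-52 50". In order, the entries are BSA band, total pill count, calculated dose and actual dose.

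In the 75 mg/m² table of the same appendix, the rows for the same two actual doses are "0.57-0.63 3 42.75-47.25 45" and "0.64-0.7 4 48-52.5 50".

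The available strengths are in Section 9.4.3: "Temozolomide capsules are available in six different strengths (5, 20, 100, 140, 180, 250 mg". Section 9.4.4 warns of overdosage that may arise from "dispensing/taking the wrong number of capsules per day". It tells the pharmacy how to proceed: "Based on the dose prescribed, determine the number of each strength of temozolomide capsules needed". It also has an instruction on labelling: "Label each container with the appropriate number of capsules to be taken each day".

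**The concern.** The two tables disagree about how many capsules make 45 mg and 50 mg, although both draw on the same set of strengths. In the 100 mg/m² table the larger dose also has the smaller count. That is not wrong in itself, because counts fall whenever a 20 mg capsule replaces four 5 mg capsules, so it has to be checked against the strengths.

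This is an operative dosing table for a cytotoxic drug. The affected bands cover small patients: Section 4.1.1 admits children from 6 months of age, and the irinotecan table in Section 5.1 goes down to a BSA of 0.25 m². The protocol itself treats capsule counts as a safety matter. A count that cannot be made up defeats the cross-check that the column is there to provide, and it could lead someone to adjust the capsules to fit the count.

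**Working it through.** **Inputs.** Strengths of 5, 20, 100, 140, 180 and 250 mg (Section 9.4.3); the 37 rows of the 100 mg/m² table and the 28 rows of the 75 mg/m² table (Appendix IV).

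**Step 1: are the milligram doses right?**
- 100 mg/m² × 0.43 to 0.47 m² = 43 to 47 mg, midpoint 45 mg.
- 100 mg/m² × 0.48 to 0.52 m² = 48 to 52 mg, midpoint 50 mg.

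Both agree with the printed calculated and actual doses.

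**Step 2: which counts can make each dose?** Only the 5 and 20 mg capsules can contribute to a dose below 100 mg. With *n* capsules in total, of which *b* are 20 mg, the dose is 5(*n* − *b*) + 20*b* = 5*n* + 15*b*.

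| Dose | *b* = 0 | *b* = 1 | *b* = 2 | Possible counts | Printed, 100 mg/m² table | Printed, 75 mg/m² table |
|---|---|---|---|---|---|---|
| 45 mg | *n* = 9 | *n* = 6 | *n* = 3 | 3, 6, 9 | 4 | 3 |
| 50 mg | *n* = 10 | *n* = 7 | *n* = 4 | 4, 7, 10 | 3 | 4 |

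The printed 4 for 45 mg and 3 for 50 mg cannot be made. The smallest possible counts are 3 (20+20+5) and 4 (20+20+5+5).

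**Step 3: does any other row fail?** All capsule combinations from the six strengths were enumerated for every row.
- 100 mg/m² table: 35 of 37 rows show the minimum possible count. The two exceptions are 45 mg and 50 mg.
- 75 mg/m² table: 28 of 28 rows show the minimum possible count.
- Together, 63 of 65 rows are right.
- The doses from 20 to 150 mg in 5 mg steps, 27 in all, appear in both tables. The counts agree for 25 of them and differ only at 45 and 50 mg.

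Exchanging the two counts brings all 37 rows of the 100 mg/m² table into line.

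**Step 4: what if someone followed the count rather than the dose?** Using 5 and 20 mg capsules:
- 4 capsules make 20, 35, 50, 65 or 80 mg. The totals nearest to 45 mg are 35 mg (35/45 = 0.78, or −22%) and 50 mg (50/45 = 1.11, or +11%).
- 3 capsules make 15, 30, 45 or 60 mg. The totals nearest to 50 mg are 45 mg (45/50 = 0.90, or −10%) and 60 mg (60/50 = 1.20, or +20%).

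The table names no strengths, so it does not determine which of these would result.

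**The case against.** The arithmetic is not open to dispute; the case against is about how much it matters.

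- **No dose is wrong.** Every milligram value is correct, and the Therapy Delivery Maps record temozolomide in mg, not in capsules. This stands.
- **Dispensing starts from the dose.** Section 9.4.4 has the pharmacy work from the prescribed milligrams to the number of each strength, and its worked example of 275 mg does so. Since the nomogram names no strengths, a total count cannot be dispensed on its own, and a mismatch will probably be noticed. This stands and is the main mitigation.
- **Labels carry counts by strength.** Section 9.4.4 requires a separate container for each strength, so the table's total appears on no single label. This makes a wrong label less likely but does not rule it out: a dispenser reconciling to 4 capsules could label two 20 mg and two 5 mg capsules, which is 50 mg for a 45 mg dose.
- **Few patients are exposed.** Sites may use a suspension for children who cannot swallow capsules, and then the count does not apply. Section 9.4.4 also allows capsules to be opened into apple sauce or juice, where they are still counted.
- **The percentages are hypothetical.** They require someone to set aside the dose printed in the same row. They show what reliance on the count could do, not an expected effect.

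An extraction fault is an unlikely explanation: the other columns in both rows are intact and in sequence, and each wrong count is exactly the neighbouring row's correct value.

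**Conclusion.** The error is certain: two cells of the 100 mg/m² table hold counts that the listed strengths cannot produce, and transposition is the natural reading. This rests only on the strengths in Section 9.4.3 and on the table as printed.

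Its effect on dose is nil where the Actual dose column is followed. If a site relied on the count, the nearest totals would be off by −22% or +11% for the 45 mg band and by −10% or +20% for the 50 mg band. Nothing in the documents shows that this has happened. Dose escalation, the definition of dose-limiting toxicity and the analyses do not use the column.

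It should be corrected all the same. Sites are sent to this table to dose small children with a cytotoxic drug, and the protocol names wrong capsule counts as a hazard.

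**What to change.** In the 100 mg/m² table of Appendix IV, change two entries in the Total pill count column:

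- BSA 0.43-0.47 m² (45 mg): from 4 to 3, made up as 20+20+5 mg.
- BSA 0.48-0.52 m² (50 mg): from 3 to 4, made up as 20+20+5+5 mg.

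Leave the calculated and actual doses as they are; the 75 mg/m² table needs no change. Send sites a short notice, since they may be working from the printed table.

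The cost is two table cells and the notice, with no change to dose, design or analysis.

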APPENDIX V: UNACCEPTABLE ENZYME-INDUCING AND RECOMMENDED NON-ENZYME INDUCING ANTICONVULSANTS

Recommended Non-enzyme inducing anticonvulsants	
Generic Name	
Clonazepam	
Diazepam	
Ethosuximide	
Ezogabine	
Gabapentin	
Lacosamide	
Lamotrigine	
Levetiracetam	
Lorazepam	
Perampanel	
Tiagabine	
Topiramate	
Valproic Acid	
Zonisamide	
Unacceptable Enzyme inducing anticonvulsants	
Generic Name	
Carbamazepine	
Felbamate	
Phenobarbital	
Fosphenytoin	
Phenytoin	
Primidone	
Oxcarbazepine	

